7.1 Specification of Safety Parameters

Table 2 Assessment and Management of Safety Issues

Safety Issue	How assessed	When Assessed in Phase 2/Phase 3	Relevant Research Staff Actions
Injuries due to yoga	Structured self-report	Weekly during first 3 months	Follow until resolution; may result in changes to yoga instructor manual
Other AEs	SAFTEE Participant report to research staff	M3 BL, M3, M6*, M12* Any point	If related to study participation, follow resolution; potential changes to procedures particularly if AE is also unexpected

*Phase 2 only

7.2 Methods and Timing for Assessing, Recording, and Analyzing Safety Parameters

See Table 2

7.3 Adverse Events and Serious Adverse Events

Adverse Event (AE) definition: An adverse event (AE) is any unfavorable and unintended diagnosis, symptom, sign (including an abnormal laboratory finding), syndrome or disease which either occurs during the study, having been absent at baseline, or if present at

baseline, appears to worsen. Adverse events are to be recorded regardless of their relationship to the study intervention.

Serious Adverse Event (SAE) definition: A serious adverse event (SAE) is one that meets one or more of the following criteria:

- Results in death
- Is life-threatening (places the subject at immediate risk of death from the event as it occurred; includes a suicide attempt or drug overdose)
- Results in inpatient hospitalization or prolongation of existing hospitalization
- Results in a persistent or significant disability or incapacity
- Results in a congenital anomaly or birth defect

An important medical event that may not result in death, be life threatening, or require hospitalization may be considered an SAE when, based upon appropriate medical judgment, the event may jeopardize the subject and may require medical or surgical intervention to prevent one of the outcomes listed in this definition.

Study staff will record all reportable events with start dates occurring any time after informed consent is obtained at least until the final day of study participation. Each time participants attend a yoga class, we will inquire about injuries due to yoga. For all participants in either the Phase 1 or 2, at Month 3 (end of intervention), study staff will administer the SAFTEE in order to inquire about the occurrence of AE/SAEs during the previous 3 months. This allows us to systematically assess number of adverse events, severity, and resulting impairment. Finally, any time a participant reports an adverse event to any staff member, a research assistant will contact the participant to ascertain information for recording of the adverse event. For adverse events ascertained by any of these three possible methods, the research assistant gets information on what happened, start and stop dates, severity, functional impact, interactions with healthcare professionals, perceived cause, and possible relation to study participation. With this information, [name] or [name], with input from Drs. [name] or [name], will code severity, causal relationship, and whether the event was expected. If necessary, staff will seek further information from the participant or other sources before coding. AEs will be coded on a weekly basis. Any potential SAE will be immediately reviewed by one of the MPIs or site PIs (or a qualified designee in their absence) and coded; this coding will subsequently be reviewed by the Safety Monitoring Committee (SMC).

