6.2.4 Follow-up Visits

For the purposes of targeting dates for an assessment, we will consider each month = 28 days (4 weeks exactly). For all follow-up assessments, research staff will make every effort to conduct the assessment within one week before or one week after the exact due date of the assessment. However, because all data can be analyzed with modern statistical methods regardless of whether it was collected inside that window, RAs will still collect data if possible even if it is later than that two-week window. We will record optimum date for the assessment (e.g., Enrollment + 84 days for M3 assessment) as well as the actual date of the assessment. Note that we will attempt to conduct follow-up visits in person, but if that is not possible, we will collect data via telephone and a REDCap link, or via telephone only (if participant does not have access to a computer/ smartphone, e.g., pre-randomization, or at M6 or M12 follow-up).

Phase 1 and Phase 2 Visits:

- Weekly for 12 weeks
 - Study classes/groups
 - Homework Questionnaire
 - Injuries due to yoga
 - CEQ (after initial class only)
 - Any other AEs reported to RAs
- Month 1
 - Any other AEs reported to RAs
 - TSK
 - Self-efficacy for exercise
 - Logistic Factors
 - BREQ-2
 - BPI
 - NRS
 - ASI
 - Penn Craving Scale
 - Payment: \$20
- Month 2
 - Any other AEs reported to RAs
 - TSK
 - Self-efficacy for exercise
 - Logistic Factors
 - BREQ-2
 - BPI
 - NRS
 - ASI

- Penn Craving Scale
- Payment: \$20
- Month 3 (Final evaluation for Phase 1)
 - Any other AEs reported to RAs
 - TRAQ
 - TSK
 - Self-efficacy for exercise
 - Logistic Factors
 - BREQ-2
 - BPI
 - NRS
 - WHOQOL-BREF
 - PROMIS® Depression Scale
 - PROMIS® Anxiety Scale
 - ASI
 - Penn Craving Scale
 - SAFTEE
 - Chart Review
 - Qualitative Exit Interview (Phase 1 only)
 - Payment: \$30

Phase 2 Visits Only:

- Month 6
 - Homework questionnaire
 - Any other AEs reported to RAs
 - TRAQ
 - BPI
 - NRS
 - WHOQOL-BREF
 - PROMIS® Depression Scale
 - PROMIS® Anxiety Scale
 - ASI
 - Penn Craving Scale
 - Chart Review
 - Payment: \$30
 -
- Month 12 (Final evaluation for Phase 2)
 - Homework questionnaire
 - Any other AEs reported to RAs
 - TRAQ
 - BPI
 - NRS
 - WHOQOL-BREF
 - PROMIS® Depression Scale
 - PROMIS® Anxiety Scale
 - ASI
 - Penn Craving Scale

- Chart Review
- Payment: \$40

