9.5 Outcomes

9.5.1 Primary/Proximal Outcome

Phase 1 is a pilot study to assess feasibility. The primary aims and outcome assessments are shown in Table 4 below.

Table 4. Targets for Phase 1 Pilot Study.		
Feasibility Area	Method of assessment	Target at each site
Recruit participants	Number recruited per month	Recruit 10 participants in 4 months.

Train yoga teachers to fidelity	Teacher fidelity scale	Each teacher demonstrates >80% fidelity on final 3 classes rated.
Randomize participants to intervention components and correctly administer these components	Randomization errors; receipt of incorrect intervention components	No errors/ incorrect components received in 2 nd half of participants randomized.
Collect follow-up assessments	Percent of follow-up assessments collected (for M1, M2, and M3)	≥ 70% with sufficient data collected on dosage; ≥ 70% of other follow-up assessments collected, including chart reviews

The proximal outcome of Phase 2 is yoga dosage received. This will be calculated by adding total number of minutes per week in the study yoga class and total number of minutes per week in personal practice (or outside yoga classes). Research staff will take attendance at study yoga classes, and, in the event someone does not attend the entire yoga class, will record the number of minutes present in class. We will measure personal practice using the Weekly Personal practice Questionnaire.

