3. Feedback from administrators/ clinicians at sites [from field notes (clinicians) and structured interviews (key administrators)]
4. Adverse events determined to be related to a given component
5. Number of 1:1 sessions attended (relevant for the 1:1 session intervention component only); use of personal practice videos (relevant for the personal practice video component only). We note that even one 1:1 session, or a small amount of use of personal practice videos, could have an impact on pain interference or other relevant outcomes.
6. % of follow-up assessments completed (not expected to be different between groups; we would consider a difference of 15% in proportion of participants observed at M3 to be of concern, and would likely be a statistically significant difference)

In determining feasibility, each component that passed Step 1 will be determined to be:

1. Acceptable and feasible without any changes.
2. There are minor changes that we judge do not affect the core nature of the intervention that we can make to increase acceptability and feasibility to a higher level (e.g., 1:1 meetings were scheduled for 45 minutes but everyone agrees that 30 minutes was adequate and even preferable).
3. Not acceptable/ feasible.

Step 3. All components that passed Step 1 and Step 2 will be included in the final optimized intervention. We will make minor changes to components if indicated in Step 2.

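### Section 7.3 asks about yoga injuries at each class attended, but Tables 1 and 2 schedule the question weekly; the plan should say that non-attenders are asked too

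*Combined protocol and SAP*

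**What the plan says.** The protocol describes the timing of the injury question in four places.

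- **Section 7.3** makes class attendance the trigger: "Each time participants attend a yoga class, we will inquire about injuries due to yoga". It adds a Month 3 interview for all participants, in which "study staff will administer the SAFTEE in order to inquire about the occurrence of AE/SAEs during the previous 3 months", and a passive route: "any time a participant reports an adverse event to any staff member, a research assistant will contact the participant". It then treats the list as complete: "For adverse events ascertained by any of these three possible methods".
- **Table 2 (section 7.1)** lists injuries as a structured self-report, timed "Weekly during first 3 months". No attendance condition is given. Section 7.2, on methods and timing, only points to Table 2.
- **Table 1 (section 6.1)** marks the injury item in the weekly column for months 1 to 3, again without an attendance condition.
- **Section 6.2.4** places "Injuries due to yoga" in the 12-week block, beside both the study classes and the Homework Questionnaire. That placement fits either reading.

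Two other parts of the plan bear on why the trigger matters. Section 9.5.1 defines the Phase 2 outcome by "adding total number of minutes per week in the study yoga class and total number of minutes per week in personal practice", so class attendance is part of the outcome, and section 5.2 has Component 4 pay $15 per class attended. In section 9.6, Step 2 of component selection considers "Adverse events determined to be related to a given component".

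**The concern.** Staff working from 7.3 and staff working from Table 2 would do different things in a week when a participant misses class: the first would not ask about injuries and the second would. With two sites, practice could also differ by site.

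Under the 7.3 rule three kinds of injury could go unasked in the week they occur: one from home practice in a week without class, one that keeps the participant away from class, and one that ends attendance altogether. Mild physical injury is the only adverse event that section 7 expects from yoga, so this is the plan's main safety item. Section 2.2 names class attendance as the chief difficulty in the pilot, so missed weeks should be expected.

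The number of times a participant is asked would also depend on something the components are meant to change. Incentives could raise the number of inquiries and so the number of injuries recorded. Components 1 and 3 encourage home practice, and an injury there in a week without class would prompt no question, so the distortion need not run in one direction. Late detection has a practical cost as well, since Table 2 has injuries followed to resolution and allows them to change the instructor manual.

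**Working it through.** **The plan's figures.** The plan states no attendance rate, injury rate or expected injury count, so there is no figure on this point to reproduce. The power statement in section 9.2 does not depend on injury ascertainment. As a check of context, with 79 per level and two-sided alpha .10, power = Φ(d × √(79/2) − 1.645). This gives 0.808 at d = .40 and 0.933 at d = .50, in line with the stated bounds. Nothing below changes that.

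**The passages side by side.**

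| Place | When the injury item is asked | Attendance condition |
|---|---|---|
| Section 7.3 | At each class attended | Yes |
| Table 2, with 7.2 deferring to it | Weekly for three months | None stated |
| Table 1 | Weekly column, months 1 to 3 | None stated |
| Section 6.2.4 | In the 12-week block, beside classes and the Homework Questionnaire | Unclear |

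**Illustration of the 7.3 rule.** The inputs are:
- 12 weekly classes (section 5.2);
- share of weeks attended, p (assumed);
- true injury rate per week, λ, equal in both groups and unrelated to attendance (assumed, 0.02 to 0.10).

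The item is taken to be asked only in attended weeks and to cover only that week.

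- Expected inquiries = 12 × p.
- Expected injuries captured by the item = 12 × λ × p.
- Apparent ratio between groups = p₁ / p₀, since λ cancels.

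| Assumed attendance, lower v higher | Inquiries | Apparent ratio |
|---|---|---|
| 45% v 50% | 5.4 v 6.0 | 1.11 |
| 30% v 40% | 3.6 v 4.8 | 1.33 |
| 40% v 60% | 4.8 v 7.2 | 1.50 |
| 30% v 60% | 3.6 v 7.2 | 2.00 |

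For example, at λ = 0.05 the true mean is 12 × 0.05 = 0.60 injuries per participant in both groups. At 40% v 60% attendance the item captures 0.60 × 0.40 = 0.24 and 0.60 × 0.60 = 0.36.

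**Effect of the other routes.** Let r be the share of injuries in missed weeks that is recovered by recall at a later class, by SAFTEE, by research-assistant contact or by spontaneous report. The ratio becomes [p₁ + r(1 − p₁)] / [p₀ + r(1 − p₀)]. At 60% v 40% it falls from 1.50 when r = 0 to 1.00 when r = 1. The documents do not allow r to be estimated, so the tabulated ratios are upper bounds for each attendance gap.

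**The weekly rule.** If every participant is asked each week and answers, p no longer enters and the ratio is 1.00.

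**The case against.** The strongest reply is that the protocol already provides for weekly questioning. Both tables schedule it, section 7.2 points to Table 2, and because classes are weekly the sentence in 7.3 may be shorthand for the weekly self-report described by its usual occasion. That reading is plausible. It is why this is an inconsistency to reconcile, and why the documents do not support the stronger inference that the plan asks only attenders about injuries. The text of 7.3 still has to change, because read as written it excludes non-attenders.

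Second, there are contacts that do not depend on attendance. SAFTEE goes to all participants at Month 3. Table 1 has an interview row for other adverse events, weekly and at each follow-up visit. Assessments continue after drop-out (6.2.5) and after discontinuation (section 8). This stands, and it makes the dependence partial. The limits are that SAFTEE is given once with three-month recall, and that 6.2.4 describes the other events as those reported to staff, which may mean no active question.

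Third, a reader might infer that the incentive group will show a 1.5-fold excess of injuries, or that Component 4 could be rejected wrongly because of it. The documents support neither. The attendance gap is assumed. Risk may also follow attendance, since the one expected event includes aches in or soon after class, so some excess among attenders could be genuine. Step 2 relies on relatedness coded event by event, with no between-group rate comparison and no adverse-event threshold, and it is one of six inputs to a judgement.

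**Conclusion.** The concern holds as an inconsistency with a partial effect on safety ascertainment. Section 7.3 conditions the dedicated injury question on class attendance; Tables 1 and 2 do not. If 7.3 is followed, non-attenders are not asked that week, and the frequency of asking varies with a quantity that Component 4 is intended to raise.

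The size cannot be fixed from the documents. Over assumed attendance gaps from 45% v 50% to 30% v 60%, the apparent ratio at equal true risk is at most 1.11 to 2.00. These bounds assume no recovery by any other route and injury risk unrelated to attendance. Alpha, power and the primary dosage analysis are unaffected. The correction is worth making because it is cheap and concerns the main expected harm.

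**What to change.** Reconcile section 7.3 with Tables 1 and 2. State in 7.3 that the injury item is asked of every participant each week for 12 weeks, together with the weekly personal-practice questionnaire and whether or not the participant attended class. Use the same statement in section 6.2.4, where the present list leaves the matter open. When component-related adverse events are reviewed in Step 2 of section 9.6, report injuries per participant-week asked, so that differences in how often people were asked are visible.

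The cost is a change of wording and brief weekly contact with non-attenders. The dosage outcome already needs that contact, because it counts personal-practice minutes in weeks without class. This takes the Homework Questionnaire of Table 1 and the weekly practice questionnaire of section 9.5.1 to be the same instrument, which the protocol should confirm.

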7.4 Reporting Procedures

Reporting for Multi-Center Trials

The site PI must immediately report to the coordinating center MPIs any serious adverse event that is possibly study related within 48 hours of PI awareness of the event. Unrelated SAEs must be reported within 7 days.

The site PI must also report any unanticipated problems (see below) within 48 hours of PI awareness of the event. The Site PI must also report any protocol violations to the coordinating center PI within 7 days of PI awareness. Participating centers must also submit all reports to their local IRB in accordance with their institutional policies.

AE/SAE Reporting

SAEs that are unanticipated, serious, and possibly related to the study intervention will be reported to the Safety Monitoring Committee (SMC), IRB, and NCCIH in accordance with requirements. We will use the Butler Hospital IRB-approved AE report form.

- Unexpected fatal or life-threatening SAEs related to the intervention will be reported to the IRB, NCCIH Program Officer, and SMC within 3 days of the investigator becoming aware of the event. Other serious and unexpected SAEs related to the intervention will be reported within 7 days. These timeframes follow guidance from NCCIH and are consistent to local IRB policies.

Anticipated or unrelated SAEs will be handled in a less urgent manner but will be reported to the SMC, IRB, and other oversight organizations in accordance with their requirements, and will be reported to NCCIH on an annual basis.

- Unrelated SAEs that are fatal or life threatening must be reported to the Butler Hospital IRB within 7 days of the investigator becoming aware of the event.
- Unrelated SAEs that are not fatal or life-threatening must be reported to the Butler Hospital IRB annually.

All other AEs documented during the course of the trial will be reported to NCCIH on an annual basis by way of inclusion in the annual report and in the annual AE summary which will be provided to NCCIH and to the SMC. The SMC Report will state that all AEs have been reviewed.

Unanticipated Problem Reporting

OHRP considers *unanticipated problems*, in general, to include any incident, experience, or outcome that meets **all** of the following criteria:

1. Unexpected (in terms of nature, severity, or frequency) given (a) the research procedures that are described in the protocol-related documents, such as the IRB-approved research protocol and informed consent document; and (b) the characteristics of the subject population being studied;
2. Related or possibly related to participation in the research (in this guidance document, *possibly related* means there is a reasonable possibility that the incident, experience, or outcome may have been caused by the procedures involved in the research); and
3. Suggests that the research places subjects or others at a greater risk of harm (including physical, psychological, economic, or social harm) than was previously known or recognized.

Incidents or events that meet the OHRP criteria for unanticipated problems require the creation and completion of an unanticipated problem report form. OHRP recommends that investigators include the following information when reporting an adverse event, or any other incident, experience, or outcome as an unanticipated problem to the IRB:

- Appropriate identifying information for the research protocol, such as the title, investigator's name, and the IRB project number;

- A detailed description of the adverse event, incident, experience, or outcome;
- An explanation of the basis for determining that the adverse event, incident, experience, or outcome represents an unanticipated problem;
- A description of any changes to the protocol or other corrective actions that have been taken or are proposed in response to the unanticipated problem.

To satisfy the requirement for prompt reporting, unanticipated problems will be reported using the following timeline:

- Unanticipated problems that are not SAEs will be reported to the IRB, SMC, and NCCIH within 14 days of the MPIs becoming aware of the problem.
- See above for SAE reporting.

All unanticipated problems should be reported to appropriate institutional officials (as required by an institution's written reporting procedures), the supporting agency head (or designee), and OHRP within one month of the IRB's receipt of the report of the problem from the MPIs.

7.5 Follow-up for Adverse Events

Any SAEs related study participation will be followed for outcome information until resolution or stabilization. Follow-up reports will be submitted to the IRB, SMC, or NCCIH as required in each specific instance.

7.6 Safety Monitoring

NCCIH requires that all Human Subjects research studies undergo independent monitoring, and NCCIH Program Officials will provide specific guidelines to the PI for the study.

8. INTERVENTION DISCONTINUATION

Participants will be discontinued from an intervention in the following circumstances:

- If a participant, their primary care provider, or their OAT provider does not believe it is in the best interest of the participant to continue. As soon as an MPI or site PI is informed of this, they will speak with the participant about discontinuation. There may be circumstances (e.g., worsening pain, an injury in yoga class) when the MPI reaches out to a primary care provider, OAT provider to actively inquire if they have concerns about the participant continuing to participate.
- If a participant chooses to discontinue attendance.
- If one of the MPIs or site PIs, in consultation with the relevant instructor, finds the participant to be so disruptive to the rest of the class that they have a repeated and substantive negative impact on the other participants.
- If a participant knowingly compromises the confidentiality of another class participant.

Participants will continue with subsequent assessments with their permission. Assessment schedule and assessments used will not change.

9. STATISTICAL CONSIDERATIONS

9.1 General Design Issues

The overall goal of this balanced factorial optimization trial is to develop a yoga intervention package that is optimized for achieving maximal “dosage” of yoga received.

We will document feasibility and acceptability of a yoga program for chronic pain at two new recruitment sites and develop a yoga intervention optimized for maximizing the dose of yoga received. We will also examine mechanisms by which components may serve to increase yoga dosage received.

9.2 Sample Size and Randomization

In RCTs a conclusion is made regarding the effect of intervention based on rejecting the null hypothesis with Type I error $<$ some predefined α . In contrast, in an optimization trial, a decision is made to include or exclude specific components in an intervention that will be tested in a future RCT. In this scenario, Type II error may be as pernicious as Type I error. Therefore, based on recommendations of Collins ³⁰ this study will be powered with $\alpha/2 = .10$. Because intervention effects are uncorrelated (or nearly uncorrelated if the design is not perfectly balanced), the alpha will not be corrected for multiple comparisons and all effects have equal statistical power. Assuming approximately 17% attrition for our primary outcome of dosage, we estimated power for $n= 158$ (192-34). To estimate the minimum detectable effect size we assumed a small correlation ($r = .15$) between recruitment site and yoga attendance and used the FactorialPowerPlan ³¹ macro in R. The proposed design has sufficient power ($1 - \beta > .80$) to detect a standardized difference in means of .40 or larger. Power to detect a medium standardized effect ($d = .50$) is $> .90$.

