9.3 Definition of Populations

All data analysis will use the intent to treat population and use all available data. There is no per protocol analysis planned.

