9.6 Data Analyses

Phase 1 Data Analysis: See Section 9.5.1

Phase 2 Data Analysis: We plan to assess 4 candidate intervention components for possible inclusion in an optimized intervention that will be evaluated in a future RCT. To do so, we will use a balanced factorial ANOVA illustrated in Table 2. Each component will have two conditions producing a $2^4 = 16$ cell design with 4 main effects, 6 possible 2-way interactions, 3 possible 3-way interactions, and 1 possible 4-way interaction. In a fully balanced design using effect coding (not dummy coding), all effects in the model are uncorrelated and the n for each condition for all effects is N/2 (i.e., 96 without attrition; 79 estimated with 17% attrition for this primary outcome). Note that specific cells are not compared against other specific cells.

We will use a general linear model with each candidate component coded using effect (1 vs -1) coding. Recruitment site, sex, age, and OAT type will be covariates. The pragmatic exigencies of field research will likely result in imperfect balance (e.g., individual cells may have slightly varying n). However, we anticipate only very small variations in cell sizes and thus estimated model coefficients will be nearly, but not perfectly, uncorrelated.

To augment traditional frequentist statistics and facilitate interpretation we will calculate the Bayes factor. Based on the observed data, a Bayes factor estimates the strength of evidence supporting one hypothesis (model) in favor of a competing hypothesis (model).³²

We will track which classes each participant attends, and who teaches each class. As a sensitivity analysis, we will include not only site as a fixed effect, but also teacher. We will include a dummy variable for each teacher to represent whether or not the participant had exposure to that particular teacher (i.e., took at least one class with that teacher).

Determination of Final Intervention Components:

Goal: To determine which components will be included in the final, optimized intervention package.

Components:

All participants: attendance at 1 class (with 2 time choices) per week; materials for personal practice

1. Personal practice videos featuring study yoga teachers
2. Initial and 1-month 1:1 session with a yoga teacher
3. Text messages cuing personal practice
4. Monetary incentives for class attendance

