Once data collection is complete, we will convene a meeting (or conference call) to make decisions about which intervention components should be included in the final intervention package. Participants in this meeting will include:

1. MPIs and co-Is and consultant [name];
2. Selected NCCIH staff (e.g., PO); and
3. Selected yoga instructors

At this meeting we will review all data collected.

Step 1: For each intervention component, we will first review the main and 2nd order interaction effects from the factorial experiment on the primary outcome of number of yoga minutes per week. We assume data will be missing at random. Missing data will be addressed using multiple imputation by chained equations.³³ Because the goal is intervention optimization, retention of components will not be based on a single criterion. We will initially choose to include all components for which there is a main or sympathetic interaction effect with a) an effect size (SMD) of 0.40 (estimated, based on preliminary data, to be 31 mins of yoga per week) or greater favoring the component; OR b) $p < .10$ favoring the component OR c) if the estimated Bayes factor provides substantial or stronger evidence preferring the intervention hypothesis to the hypothesis of no treatment effect. (See below for more information on Bayes factor).

Special cases:

1. Of monetary incentives for class attendance, we will look specifically at class attendance. If monetary incentives increase class attendance, and do not decrease overall minutes of practice, we will choose to include.
2. 3rd and 4th order interactions may be tricky to interpret. We will look at them, but place priority on main effects and 2nd order interactions in making decisions.
3. It is possible that 2nd order interactions may be antagonistic where the combination of two or more components is less effective than would be expected based on the main effects alone. At the same time, there may be significant positive main effects for both components. In this case, we will examine graphical depictions of results in order to determine whether to include both of the two components in question.

Step 2: All components that pass Step 1 will then be examined in light of their feasibility and acceptability. Data that bear on feasibility and acceptability include:

1. Participants' responses to qualitative interviews
2. Yoga instructors' experiences (field notes)

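### Section 9.2 prints α/2 = .10 (two-sided .20), but its detectable effect of .40 at n = 158 matches two-sided α = .10, as does the natural reading of Step 1(b)

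*Combined protocol and SAP*

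**What the plan says.** Section 9.2 (Sample Size and Randomization) argues that in an optimization trial a Type II error can do as much harm as a Type I error, and on that ground relaxes the significance level: "this study will be powered with $\alpha/2 = .10". There is no multiplicity correction. After about 17% attrition, power is computed for 158 of the 192 enrolled. The purpose is given as "To estimate the minimum detectable effect size". The result is power above .80 "to detect a standardized difference in means of .40 or larger", with power above .90 at .50. A correlation of .15 between site and attendance was assumed, and the FactorialPowerPlan macro was used.

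Section 9.6 (Data Analyses) specifies the model: "We will use a general linear model with each candidate component coded using effect (1 vs -1) coding". Step 1 retains a component if any one of three criteria is met: (a) an SMD of at least 0.40, "estimated, based on preliminary data, to be 31 mins of yoga per week"; "OR b) $p < .10$ favoring the component"; or (c) a sufficiently strong Bayes factor. Whether p is one- or two-sided is not stated.

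Two statements bear on the effective sample size. Section 9.3 says "All data analysis will use the intent to treat population and use all available data", and Step 1 adds "Missing data will be addressed using multiple imputation by chained equations".

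**The concern.** Section 9.2 is the only place where the design alpha is stated, and relaxing that alpha is what the paragraph argues for. The printed value is twice the one that fits the paragraph's own detectable effect.

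It also sits poorly with the decision rule. The usual p-value for a general linear model coefficient is two-sided, and the words about favouring the component then add a condition on the sign. That is a two-sided .10 rule. A reader who brings Step 1(b) into line with 9.2 as printed would instead use one-sided p < .10.

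Because the Step 1 criteria are joined by OR, passing (b) alone is enough to pass Step 1 initially. The rate at which an ineffective component passes (b) is therefore uncertain by a factor of two. If this is left open until the data are reviewed, the tail could be chosen after the results are known.

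**Working it through.** **Inputs.** From 9.2: n = 158 analysed, power .80, effects .40 and .50, r = .15. From 9.6: an even split on each component (79 v 79), and 0.40 SMD = 31 min/week. With ±1 coding and an even split, the standard error of a standardized main effect is SE = 2/√n.

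- n = 158: 2/√158 = 0.1591
- n = 192: 2/√192 = 0.1443

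**Reproducing the plan's .40 (n = 158, normal approximation).** Minimum detectable effect = (z for α + z for power) × SE.

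- Two-sided .10: (1.645 + 0.842) × 0.1591 = 0.396
- Literal α/2 = .10: (1.282 + 0.842) × 0.1591 = 0.338
- Two-sided .05: (1.960 + 0.842) × 0.1591 = 0.446

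Power = Φ(effect/SE − z for α). At .40, effect/SE = 0.40/0.1591 = 2.514.

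- Two-sided .10: Φ(2.514 − 1.645) = .808
- Literal α/2 = .10: Φ(2.514 − 1.282) = .891

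**Noncentral t check.** The t calculation used 138 to 156 degrees of freedom. It was run without the site correlation and with it treated as a covariate correlation, so that SE is multiplied by √(1 − .15²).

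| Alpha, n = 158 | Minimum at 80% power | Power at .40 | Power at .50 |
|---|---|---|---|
| two-sided .10 (α/2 = .05) | .393–.398 | .804–.812 | .931–.936 |
| literal α/2 = .10 | .335–.339 | .890–.895 | .968–.971 |
| two-sided .05 | .443–.449 | .704–.715 | .877–.885 |

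Of these, only two-sided .10 (numerically the same as one-sided .05) gives .40 as the minimum. Two-sided .05 fails both stated powers. With all 192 analysed, two-sided .05 gives a minimum of .402–.407, but power at .40 is .787–.796. That is short of .80, and 192 is not the n the plan used.

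**Solving back for alpha.** For .40 to be the exact 80% minimum at n = 158, z = 2.514 − 0.842 = 1.672, which is a two-sided α of .0945. The noncentral t gives .0969 with r = 0 and .0914 with r = .15.

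**Solving back for n.** At .40 and 80% power, n = (2 × (z for α + z for power)/0.40)².

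- Two-sided .10: (2 × 2.487/0.40)² ≈ 155
- Literal α/2 = .10: (2 × 2.124/0.40)² ≈ 113

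The planned 158 fits the first.

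**Effect on Step 1(b).** A null main effect passes in the favourable direction with probability .10/2 = 5% if p is two-sided, and 10% if p is one-sided. The smallest estimate that passes is z × SE. It is converted to minutes with the implied SD of 31/0.40 = 77.5 min/week.

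| n | p two-sided < .10 | p one-sided < .10 |
|---|---|---|
| 158 | 1.645 × 0.1591 = 0.262 (20.3 min) | 1.282 × 0.1591 = 0.204 (15.8 min) |
| 192 | 1.645 × 0.1443 = 0.237 (18.4 min) | 1.282 × 0.1443 = 0.185 (14.3 min) |

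The n = 192 row is an outer limit, reached only if imputation recovered all the missing information.

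**The case against.** The best defence is that no stated figure is false. Powers above .80 and .90 are inequalities, and both hold under the literal alpha. The results sentence does not itself call .40 the minimum, and .40 is also the Step 1(a) threshold, so it may be a target chosen in advance and checked for adequate power. This stands. It is why the mismatch is strong evidence of a misprint rather than proof. Against it, the paragraph announces a minimum detectable effect, and .40 is the only figure it offers as the answer.

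Second, the rationale in 9.2 can be read as favouring the literal value. With 10% in the favourable tail, the Type II error at .40 is about 11%, so the two errors are nearly equal. Under two-sided .10 they are 5% and about 19% to 20%. That is a fair point about intent, but 9.2 does not say that it aims to equalise them.

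Third, Step 1(b) states no sidedness, and a one-sided p < .10 would agree with the literal α/2 = .10. So Step 1(b) supports the two-sided reading without settling it.

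Fourth, the macro was not run here, and the plan does not say how r = .15 entered it. For the literal alpha to give .40, the error variance would have to be about (0.40/0.338)² = 1.40 times larger. Nothing in the documents describes such inflation.

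**Conclusion.** The concern holds. At n = 158 the printed alpha implies a minimum detectable effect of about .34. The reported .40 corresponds to two-sided α = .10, which is also the natural reading of Step 1(b). One of the two figures in 9.2, or the description of .40 as a minimum, needs correcting.

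The practical size is a factor of two in the false-pass rate for a null main effect under criterion (b), 5% against 10%. The cut-off differs by about 0.06 SMD at n = 158, or roughly 20 against 16 min/week. The trial is not underpowered under either reading. No change in the final package is shown, because retention also depends on the effect size, the Bayes factor, interactions, the attendance rule for incentives, and Step 2.

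These figures assume an even split on each component, an SD of 77.5 min/week implied by the plan's own conversion, and a site correlation that either has no effect on the error variance or reduces it slightly.

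**What to change.** Check the existing FactorialPowerPlan input and output for the alpha that was entered, then make one of two edits.

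- **If two-sided .10 was used:** in 9.2, replace the printed expression with two-sided α = .10 (α/2 = .05). In Step 1(b), state that p is that two-sided value and that the estimate must favour the component. The .40 and the power statements stay as they are.
- **If α/2 = .10 was used:** in 9.2, restate the minimum detectable effect as about .34. Make Step 1(b) explicitly one-sided p < .10.

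The edit should be made before the Phase 2 results are reviewed. The cost is one check of existing output and two lines of text, with no change to sample size or data collection.
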